- Pain related disability using the Manchester Orofacial Pain Disability Scale [62]
- Oral health related quality of life using the Oral Health Impact Profile [63].
- Self-efficacy around dental visiting will be measured using an item adapted from Armitage et al 64]: '*How confident are you that you will be able to attend a dental appointment*?' (1, no confident; 7, very confident).
- Self-esteem using the Rosenberg Self-esteem Scale (RSES; [65])
- Dental anxiety using the Modified Dental Anxiety Scale [66]

- Depression using the Patient Health Questionnaire [67]
- Quality adjusted life year using the EuroQol 5 Dimension (EQ-5D-5L [68])

At baseline, we will assess bruxism using items from Aggarwal et al [69]: 'Do you grind you teeth during the day or at night?' Yes/No. 'Has someone told you that you grind your teeth?' Yes/No and hyposalivation through the item 'Does your mouth usually feel dry?' Yes/No [X] for descriptive purposes. The Mini International Neuropsychiatric Interview [71](excluding suicidal behaviour, antisocial personality disorder or eating disorder subscales) will be included as a baseline measure to assess mental health diagnosis and understand the diagnostic composition of the sample.

Demographic and clinical information will include ethnicity, diagnosis, medication, illness length, inpatient admissions, service, cigarette/substance/alcohol use (items from [72]). We will assess attendance at urgent dental services, GP, A&E, or mental health wards, and prescription of antibiotics or painkillers. To assess the feasibility of assessing clinical information as secondary outcomes for a main trail, we will also collect data on whether the person has access to free dental care, is currently on a dentist list, the number of routine dental visits, and data on self-management, namely use of *brushing, flossing, and mouthwash*. We will record data on the number and length of intervention related activity (e.g. delivery, clinical note keeping, clinical supervision) to calculate estimates of the costs of the intervention.

Assessment	Baseline	Nine month follow-up
Demographic information	\checkmark	
Background clinical information	\checkmark	
Updated clinical information		\checkmark
Self-report dental visiting	\checkmark	\checkmark
BSA recorded dental visiting	\checkmark	\checkmark
Decayed, missing, or filled teeth (DMFT): Dental examination	✓	✓
Pulpal involvement, ulceration due to trauma, fistula, and abscess (PUFA): Dental examination	✓	✓

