The dental therapist will carry sufficient sets of sterile instruments to ensure that there are sterile instruments for every examination. Following the examination these will be placed in a sealed container for transport back to the clinical base where the instruments will be sterilized according to local procedures. The dental therapist will wear a clean pair of latex free gloves and fluid resistant face mask for the examination of each participant. These will be disposed of into a standard clinical waste bag with any tissues and wipes after the exam. This will be disposed of on return to the clinic in line with normal clinical waste arrangements.

Measurements

DMFT score

An examination for dental caries in permanent teeth will involve examining 32 teeth (i.e. all permanent teeth including wisdom teeth) with a metallic periodontal probe (Community Periodontal Index (CPI) probe) and a plane mouth mirror. The permanent dentition status of each tooth (crown and root) will be recorded as a score from the above chart as follows:

- 0: Sound A crown/root is coded as sound if it shows no evidence of treated or untreated clinical caries. The stages of caries that precede cavitation, as well as other conditions similar to the early stages of caries, are excluded because they cannot be reliably identified in most field conditions in which epidemiological surveys are conducted.
- 1 = Natural tooth present with arrested caries
- 2 = Natural tooth present with caries into dentine
- 3 = Natural tooth present with caries into the pulp/retained roots
- 4 = Natural tooth present with filling(s) and caries
- 5 = Natural tooth present with filling(s)
- R = Natural tooth present with filling(s) need replacing
- 6 = Natural tooth missing, any reason, with no replacement
- C = Natural tooth with a crown
- F = Natural tooth replaced by bridge pontic, implant pontic or implant
- D = Natural tooth replaced by denture tooth

Individual DMFT value is the sum of the number of D (Decayed), M (Missing) due to caries, and F (Filled) teeth in the permanent teeth. The D component includes all teeth with codes 1, 2, 3. or 4. The M component comprises teeth coded 6. The F component includes only teeth with code 5, R or C. Teeth coded F or D (fixed dental prosthesis/bridge abutment, special crown or veneer/implant) are not included in calculations of DMFT.

PUFA score:

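### DMFT defines M as teeth missing due to caries but scores it from a code for teeth missing for any reason, over 32 teeth including wisdom teeth

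*Protocol*

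**What the plan says.** All the relevant text is in Protocol section 12, under Measurements, DMFT score.

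- Definition: "Individual DMFT value is the sum of the number of D (Decayed), M (Missing) due to caries, and F (Filled) teeth in the permanent teeth".
- Scoring rule, in the same paragraph: "The M component comprises teeth coded 6".
- Meaning of that code: "6 = Natural tooth missing, any reason, with no replacement".
- Teeth in scope: "examining 32 teeth (i.e. all permanent teeth including wisdom teeth").
- Replaced teeth: codes F (bridge or implant) and D (denture) "are not included in calculations of DMFT", whatever caused the loss.

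Table 1 lists "Decayed, missing, or filled teeth (DMFT): Dental examination" at baseline and at nine months. Section 20 plans no efficacy analysis and summarises outcomes by, for example, mean and SD to inform a definitive trial. Key output 4 in section 7 is outcome and retention data for that trial's sample size calculation. The SAP supplied is for a different trial, in university students with suicidal experiences, and has no DMFT rule.

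**The concern.** The definition asks why a tooth is missing. The scoring rule does not, because code 6 records absence from any cause provided the tooth has not been replaced. A tooth lost to injury, orthodontic treatment or gum disease and not replaced is therefore counted as though caries had taken it.

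Wisdom teeth could make this common. They are among the 32 teeth scored, and code 6 is the only printed code for an absent, unreplaced tooth. Nothing printed covers a tooth that has not erupted or never formed. The plaque score in the same section, by contrast, has a code N for sites that cannot be measured.

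At stake is the meaning of the DMFT mean and SD. If they go forward as summaries of caries experience, they also contain between-person variation in absences unrelated to caries. Two examiners, or this trial and the next, could follow different halves of the same paragraph and produce scores that are not comparable.

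**Working it through.** The documents give no DMFT figure to reproduce, so the check applies the written rule to example mouths and compares the result with the protocol's own definition.

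**Rule as written.** With n(·) the number of teeth carrying each code:

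DMFT = n(1, 2, 3, 4) + n(6) + n(5, R, C)

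Codes 0, F and D contribute nothing.

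**Rule as defined.** The D and F components are unchanged. M is the number of teeth lost to caries.

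**Difference.** Let k be the number of teeth absent for a non-caries reason, unreplaced and coded 6. Let r be the number lost to caries and replaced (chart code F or D). Then

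DMFT(written) − DMFT(defined) = k − r

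**Example mouths of 32 teeth** (assumed, not from the documents):

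| Mouth | Written | Defined | k − r |
|---|---|---|---|
| 28 sound; 4 wisdom teeth absent, not caries | 4 | 0 | 4 − 0 = +4 |
| 24 sound; 4 premolars and 4 wisdom teeth absent, not caries | 8 | 0 | 8 − 0 = +8 |
| 22 sound; 10 lost to caries, unreplaced | 10 | 10 | 0 − 0 = 0 |
| 22 sound; 10 lost to caries, on a denture | 0 | 10 | 0 − 10 = −10 |
| 18 sound; 10 lost to caries, on a denture; 4 wisdom teeth absent, not caries | 4 | 10 | 4 − 10 = −6 |

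Four wisdom teeth give k from 0 to 4 from that source alone. The last two rows show why the sign of the total error is not fixed.

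**Spread.** Take r = 0 and let X be the score as defined. Then Var(written) = Var(X) + Var(k) + 2 Cov(X, k). The documents give neither Var(k) nor the covariance, so the SD can move either way.

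**Change over nine months.** The error in change is Δk − Δr, so an offset that stays constant cancels. Single-tooth events score as follows:

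- Carious tooth extracted, unreplaced: codes 1–4 to 6, change 0.
- Sound tooth extracted for a non-caries reason, unreplaced: 0 to 6, change +1.
- Wisdom tooth erupting sound, if it had been coded 6: 6 to 0, change −1.
- Missing tooth replaced during follow-up: 6 to F or D, change −1.

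The documents give no frequency for any of these.

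**28-tooth sum.** Leaving out wisdom teeth takes the first mouth from 4 to 0, but the second only from 8 to 4. It removes the wisdom-tooth part and leaves other non-caries losses in M.

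**The case against.** The strongest reply is that little depends on this score. The proposed primary outcome is planned dental appointments. The relevant progression criterion in section 12 is the percentage completing the examination, not the score it yields. There is no efficacy test to distort, and a stable offset cancels in within-person change. All of that stands, and it limits the importance of the point.

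It is also fair to say that the treatment of unerupted teeth is an inference. Section 12 refers to a chart and a CRF that are not in the supplied text, and either could hold a further code. That qualifies the wisdom-tooth range. It does not remove the contradiction, because the protocol still puts every code 6 tooth into M and still says the cause can be anything.

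Three stronger readings are tempting, and the documents support none of them:

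- *Mean DMFT is overstated by a predictable number of points.* No distribution of absent wisdom teeth is given. Some absent wisdom teeth will have been lost to caries and belong in M. Replaced caries losses pull the other way.
- *Every non-caries loss adds a point.* Only unreplaced losses do.
- *The link-work arm will appear to develop more caries because its participants see a dentist more often.* Nothing in the protocol shows that non-caries extractions would be more frequent in that arm, and extracting a carious tooth leaves DMFT unchanged.

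**Conclusion.** The contradiction is real, and nothing in the supplied documents resolves it. Followed literally, the rule adds 1 point for each unreplaced tooth absent for a non-caries reason, contrary to the stated meaning of M. Absent wisdom teeth can contribute 0 to 4 of those points per person, on the assumption that no separate code exists on the chart or CRF that were not supplied.

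The consequence is a DMFT level that does not match its definition, and possibly a distorted between-person SD in the data meant to inform the definitive trial. The net direction for total DMFT cannot be stated, and no bias between arms is shown. The effect on this feasibility trial's own conclusions is modest. It is still worth correcting, because the rule is wrong as written and the correction is cheap.

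**What to change.** Make the definition and the scoring rule agree, state how unerupted, never-formed and replaced teeth are handled, and apply the same rule at both visits. Either of two routes would do.

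1. **Keep M as loss from caries.** Add a chart code for teeth that are unerupted, never present, or known to be lost for a non-caries reason, and leave that code out of M. The cost is one code and a question about cause of loss. The cause will sometimes be uncertain, and it cannot be recovered for teeth already charted. This route corrects only the cause of loss, so the definition should also say that replaced teeth are not counted, if that is intended.

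2. **Change the label.** Call M missing from any cause, unreplaced. Report DMFT on 28 teeth, computed from the tooth-level codes, with the 32-tooth sum beside it. This needs no new examination and works for data already collected. The cost is that carious wisdom teeth leave the 28-tooth total, and the score can no longer be presented as purely caries experience.

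If the chart or CRF already has a code for unerupted teeth, print it in section 12 and state that it is outside M.

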Some personal data will need to be shared with the Business Services Authority (first initial, surname, date of birth, gender and postcode) for the purpose of extracting data on dental attendance for each participant. LCTC will be in charge of submitting the BSA application and linking the extracted data to the master data file (research data), with support from the co-applicants (VA, JPC). NHS sites will provide LCTC with this personal data via a secure file transfer. LCTC will then submit the combined persona data from across NHS Trusts to the BSA who will extract and transfer the data on dental visiting to the LCTC. LCTC will then link this data to the research master data file.

The BSA will not have access to any research data. They will be required to keep any data secure and confidential. Personal data will be transferred securely between LCTC, NHS Trusts and the BSA. The BSA and LCTC will delete the personal data once information on dental attendance has been extracted and linked to the master datafile. We will gather informed consent from participants to use their data in this way (see consent form and PIS).

20. Statistical analysis

A full detailed statistical analysis plan will be developed prior to the analysis of the trial, following the standard operating procedures from LCTC. We will analyse data at the end of the last follow-up assessment, reporting outcomes in line with the updated CONSORT 2010 Statement for randomised pilot and feasibility trials, summarising recruitment and attrition rates, willingness to be randomised, and loss to follow-up. Analyses of intervention efficacy will not be investigated, but outcome data will be summarised to inform a definitive trial (e.g. mean, *SD* of outcomes).

The statistical analysis for this feasibility study will summarise the quantities specified in the feasibility criteria (recruitment rates, available BSA data, completed dental examinations, interventions received). These will be presented as percentages, with 95% confidence intervals. Proposed outcome measures for a full trial will be presented descriptively (e.g. mean and standard deviations). There are no covariate adjustments in the feasibility analysis.

21. Data monitoring

As this is a low-risk feasibility trial, we will not form a Data Monitoring Committee for the feasibility trial. Instead, given the small scale of the trial, data will be regularly monitored by the TSC and LCTC.

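### DMFT counts a lost tooth only while the gap is unfilled, so fitting a denture lowers the score with no change in disease

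*Protocol*

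**What the plan says.** The DMFT score part of Protocol section 12 (Measurements) has 32 teeth examined, each given one code. Three codes describe a natural tooth that has been lost:

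- "6 = Natural tooth missing, any reason, with no replacement"
- "F = Natural tooth replaced by bridge pontic, implant pontic or implant"
- "D = Natural tooth replaced by denture tooth"

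The score is then built from components. Decayed takes codes 1 to 4 and filled takes codes 5, R and C. For missing, "The M component comprises teeth coded 6". The rule closes with "Teeth coded F or D (fixed dental prosthesis/bridge abutment, special crown or veneer/implant) are not included in calculations of DMFT". The sentence that introduces the score defines the missing component differently, as "M (Missing) due to caries".

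Table 1 schedules "Decayed, missing, or filled teeth (DMFT): Dental examination" at baseline and at nine months. Protocol section 20 rules out efficacy analysis but says that "outcome data will be summarised to inform a definitive trial", with means and SDs as the example.

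The protocol contains no other DMFT rule. The supplied SAP is for a different trial, of an imagery intervention in university students, and does not mention DMFT.

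**The concern.** Codes 6, F and D all record the same biological fact, that the natural tooth is gone. They differ only in whether something fills the space. Because only code 6 enters the score, replacing a lost tooth removes it from DMFT, although no disease has been reversed.

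The resulting order is perverse. A decayed tooth scores 1. It still scores 1 if it is filled or crowned, and 1 if it is extracted and left as a gap. If it is extracted and replaced by a denture tooth it scores 0, the same as a sound tooth.

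This matters here for two reasons. The background section reports that total tooth loss is more than three times as likely in people with severe mental illness. The eligibility criteria also list dentures and bridges among the treatments that count as planned dental care, which is the care the intervention promotes. The score can therefore fall because that care was delivered. It can also rank a toothless person with dentures as healthier than a toothless person without them. If the rule were carried into a definitive trial, it could favour an arm with more denture fitting.

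**Working it through.** The protocol gives no DMFT value, so there is no figure to reproduce. The check is a direct count under the written rule.

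**Inputs from the protocol:** 32 teeth examined and the code list (section 12); 42 participants per arm (section 13). **Assumed:** the number of teeth on a complete set of dentures, taken as 28 with a range of 24 to 32, and 14 for a single arch.

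**As written:** DMFT = (number coded 1 to 4) + (number coded 6) + (number coded 5, R or C). Codes 0, F and D add 0.

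**Alternative:** the same, with missing = codes 6 + F + D.

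| Mouth | Codes | As written | 6 + F + D |
|---|---|---|---|
| Toothless, no dentures | 32 × 6 | 32 | 32 |
| Complete dentures, 24 teeth | 24 × D, 8 × 6 | 8 | 32 |
| Complete dentures, 28 teeth | 28 × D, 4 × 6 | 4 | 32 |
| Complete dentures, 32 teeth | 32 × D | 0 | 32 |
| One arch replaced, 14 teeth | 14 × D, 18 × 6 | 18 | 32 |
| Invented mixed mouth: 10 gaps, 5 decayed, 3 filled | 10 × 6, 5 × 2, 3 × 5, 14 × 0 | 18 | 18 |
| Same mouth, 6 gaps filled by denture teeth | 6 × D, 4 × 6, 5 × 2, 3 × 5, 14 × 0 | 12 | 18 |

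**Effect on an arm mean:**

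- Per replaced tooth: 1/42 = 0.024.
- Per 14-tooth denture: 14/42 = 0.33.
- Per complete set (28 teeth): 28/42 = 0.67 if all 42 are examined. If examination completion were only at the 80% green threshold, 0.80 × 42 = 33.6, about 34, and 28/34 = 0.82.

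**Bridges are not one-directional.** A pontic moves a gap from code 6 to F (−1). If two previously sound abutments are crowned and coded C, that adds 2, for a net of +1. If abutments are instead left out, as the bracket in the rule suggests, the net is −1. The claim is therefore limited to dentures.

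**Wording conflicts in the same paragraph:**

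- The bracket glosses codes F and D as abutments, special crowns, veneers and implants. In the code list F is a pontic or implant and D is a denture tooth; abutments, special crowns and veneers appear under neither. This does not rescue the rule, because a denture tooth is not code 6 and so falls outside the missing component on either reading.
- The missing component is said to be loss through caries, but code 6 covers loss for any reason and no code records cause. A caries-only component cannot be computed from these data.

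**The case against.** The strongest case is about consequence. DMFT drives no progression criterion: the clinical examination criterion concerns completion, not the score. It plays no part in the sample size, no efficacy analysis is planned, and the proposed primary outcome for the definitive trial is planned appointments. Harm needs the rule to be carried forward and denture fitting to differ between arms. The drop from 32 to 4 is an extreme case with an assumed denture size. The nine-month window is justified as long enough for a treatment course to have started, so new complete dentures within it are not shown to be common. If missing meant loss through caries, the starting value could be below 32. The CRF and this trial's own SAP were not available and might hold a different derivation.

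Most of this stands as a limit on size. It does not remove the fault. A person who already wears dentures at baseline is misranked without any treatment in the window, and the per-tooth effect applies to partial dentures too. An unseen document cannot be relied on to correct a rule that the protocol states explicitly.

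One objection bears on the remedy. If some examiners followed the bracket and recorded abutments or veneered teeth as F, adding F to the missing component would count teeth that are present as lost. That calls for a check of how F was used. It does not affect code D.

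**Conclusion.** The concern holds. As written, a lost tooth scores 1 when unreplaced and 0 when a denture replaces it. For a toothless person, complete dentures lower DMFT by 28 points if 28 teeth are replaced, and by 24 to 32 points across the assumed range. Each such wearer shifts a 42-person arm mean by 0.67.

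The direction of the denture effect follows from the codes alone. The size depends on the assumed number of denture teeth and on reading code 6 as loss for any reason. The documents give no denture uptake, so no between-arm difference can be stated. No decision in this feasibility trial is affected. What is affected is the meaning of the DMFT mean and SD passed to the definitive trial. It should be fixed before those summaries are produced.

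**What to change.** - Score the missing component as codes 6 + F + D.
- Delete the bracket that does not match the code list. Before F is added, confirm that examiners used it only for pontics and implants.
- Describe the missing component as teeth lost for any reason, and state that DMFT is then an index with all-cause tooth loss. If the team wants loss through caries, the cause of each loss would have to be recorded, because the present codes cannot supply it.
- Put the derivation in this trial's own SAP.
- Optional: report the decayed component (codes 1 to 4) separately, and a 28-tooth DMFT.

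The cost is scoring wording, derivation code and the check on F. The tooth-level codes are already collected, the examination does not change, and the correction can be made at analysis. The downside is that the index is no longer specific to caries, which must be stated wherever it is reported.

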Researchers undertaking the clinical assessments will be blind to the treatment allocation. We will monitor and record all breaking of the blind on a structured form. The senior management team and TSC will review blind breaks to establish and implement learning and reduce further blind breaks. Where possible, when one researcher becomes unblinded, a second unblinded researcher will complete the assessment. Deliberate un-blinding of the researchers during the trial is unlikely, but will be considered by the senior management team and could occur in cases of risk or safeguarding.

18. Data collection methods

Research staff and a dental therapist will collect data at baseline and after nine months. This will be in the form of questionnaires and interviews (see assessments). Self-report assessments and the dental examination will be employed face-to-face. Should face-to-face contact be difficult, we will allow for remote assessment (e.g. telephone, web platform) for the self-report measures (in such instances, dental exam data will be completed separately or treated as missing). We will provide training to research staff in standardised approaches to data collections. We will train staff in the MINI diagnostic interview and record a subset of interviews, which will be rated by a second researcher to ensure good interview technique, standardised questioning, and reliability of scoring.

Participant retention will be supported by regular telephone "check-ins" with participants involved in the trial. We will arrange these between follow-up assessment time-point to remind the participant of upcoming assessments and to give them the opportunity to ask questions. We will disseminate a study newsletter to current participants providing general information on the progress of the study and related news.

19. Data management

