Eight quarterly panel meetings will allow for discussion of liaison strategies with services, recruitment planning, sensitivity training for research and clinical staff, co-development of training materials for staff, discussion of operational and implementation issues, the refinement of the intervention, and dissemination outputs. PPI panel members will be active stakeholders making key decisions around the project, weighing up the advantages and disadvantages of certain choices. We will ensure that members all members are supported and given the opportunity to participate, making necessary adaptions where necessary (e.g. translator, large font handouts etc.). We will offer reimbursement for time and travel expenses (based on INVOLVE rates). They will receive £40 reimbursement per two-hour PPI session, plus up to 40 miles travel expenses (equivalent to £18 in travel expenses per visit). Where access is difficult, members may attend virtually via Teams/Zoom, or over speaker phone. At times, we will invite research (e.g. research assistants, dental therapist) and clinical (e.g. link workers) staff to attend PPI meetings for shared learning and discussion, whilst carefully ensuring that there is no breaking of the blind. We have costed in some time of a graphic designer who will meet with the PPI panel to co-produce an InfoGraphic of the study findings for dissemination. We will work with the PPI panel to identify any training needs during the project, which will be offered by an appropriate team member. This could include a general introduction to the research cycle or more detailed information on any aspect of the project protocols (e.g. how the dental examination works). We have costed in for three training sessions across the project. The team are experienced at offering training to service user panels and co-developing accessible outputs around protecting the oral health of people experiencing SMI (see www.rightfromthestart.com for examples).

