CL will chair the PPI panel meetings. DS (PPI carer) is a family member and retired GP and will offer a carer perspective at meetings. With member's consent, an administrator will take minutes of the PPI panel meetings so that no information is lost. PPI discussions will be brought and considered within management and steering group meetings. CL will also make a systematic record of key decisions and how this influenced the delivery of the trial and intervention. The team has an excellent record of co-development and supporting service users on PPI panels. CL is experienced at leading PPI panels.

33. Embedded qualitative study

We will conduct an embedded qualitative study that draws on the MRC evaluation of complex intervention framework [78]. This highlights the need to identify and address potential challenges that could undermine the conduct of the full RCT and/or the acceptability and delivery of the intervention. The aim is to understand the potential factors impacting (e.g. facilitators and barriers) acceptability and delivery of the support work intervention and project (research aim 5).

In particular, it aims to understand:

- a) What determines staff levels of referral
- b) Reasons for participation/non-participation during the recruitment process
- c) The feasibility of blinding RAs
- d) Support worker experiences of and attitudes to delivering the intervention
- e) Patient experiences of, and attitudes to, trial participation including any changes in behaviour
- f) How to optimize the acceptability and feasibility of a future definitive trial

These findings will be used to further refine the intervention and trial procedures based on staff and patients' feedback, and to inform the design of a definitive RCT [79].

Stages of data collection:

Work *before and during* the feasibility trial will focus on addressing aims a), b) and c) related to trial processes

- Interviews with the three RAs on the acceptability of trial recruitment and procedures
- Interviews with up to 10 service users on the acceptability of trial recruitment and procedures
- Audio-recordings of assessment sessions with RAs to identify potential issues
- Field notes from RAs and support workers.

Work *towards the end of the trial* will focus on aims d), e) and f) to understand the acceptability and feasibility of delivering the intervention

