We will work with the service user researcher (CL)/ carer advisor (DS), and PPI panel, to codevelop all information materials to ensure that they are easy to follow and understand. This will include a participant information sheet outlining the inclusion/exclusion criteria, the aims of the study, what taking part would involve, the advantages and disadvantages of taking part, confidentiality of data, information on dissemination, the details of the site RA and senior team members, and relevant complaints procedures. We will ensure that all participants have access to the participant information sheet prior to taking part. Copies will be sent via letter, email, in person, or through the referring clinical team. We will also generate plain-English recruitment posters for patients and leaflets for clinicians at recruiting sites. We have previously found that these help to generate referrals and support access to research. Senior investigators (JPC, RH), the trial manager, and the local independent research and development office (LSCFT, PCFT, GMMH) can answer any queries, concerns, or issues that participants might have with the project, intervention, or assessments, which will be clearly stated in the participant information materials. In the event that participants would prefer to talk to another agency, we will signpost them to their secondary care mental health team or the Patient Advice and Liaison Service (PALS). RAs and support workers will remind participants of their options, which will also be stated on dissemination materials, whilst emphasising the importance of maintaining blinding. At each assessment session, participants will be provided with a wallet-sized card containing the details of helplines (e.g. MindInfo Line, Samaritans, SANEline, NHS111). This will also remind participants to direct concerns about their mental health to their clinical service and to contact accident and emergency services or a crisis team in cases of emergency. Participants will have the right to withdraw from the study at any time, without it affecting their routine clinical care. If a participant wishes to withdraw, we will ask for their reasons to understand their experiences. We will ask whether participants to still consent to their existing data being used in the research or removed completely. Participants are able to withdraw from the intervention, but still complete the follow-up assessments and a qualitative interview.

35. Project / research timetable

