# Non-compliances (Protocol deviations)

Non-compliance will include blind breaks, deviations in delivery of intervention, deviations in conducting assessments and deviations in data management. Deviations are logged and severity is judged by the research team.

Serious non-compliances will be line listed and their number and type will be reported by trial arm.

If there are any serious breaches these will also be line listed.

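### Protocol Section 17 commits to blind assessors, but its only reassignment rule gives the assessment after a blind break to a second researcher described as unblinded, almost certainly a slip for blinded

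*Protocol*

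**What the plan says.** Protocol Section 17 starts with the governing commitment: "Researchers undertaking the clinical assessments will be blind to the treatment allocation". It then sets out what follows if the blind is broken:

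- Every break is recorded on a structured form.
- The senior management team and the TSC review the breaks, so that lessons are learned and the trial can "reduce further blind breaks".
- Where possible, "when one researcher becomes unblinded, a second unblinded researcher will complete the assessment".

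The section closes by saying that deliberate unblinding is unlikely but could occur for reasons of risk or safeguarding.

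Blinding comes up in three other places in the protocol. Section 32 lets research and clinical staff attend PPI meetings while "carefully ensuring that there is no breaking of the blind". Section 34 has research assistants and support workers remind participants whom they can approach with concerns, "whilst emphasising the importance of maintaining blinding". Section 33 lists "The feasibility of blinding RAs" as aim c) of the embedded qualitative study.

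**The concern.** The third step is an operative instruction to trial staff. An assessor who knows the allocation is replaced in order to get the assessment done by someone who does not. The sentence as printed names the wrong kind of replacement. Followed to the letter, it would produce an unblinded assessment at the one moment when the protocol is trying to avoid one.

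Two uses of the information are touched. First, under Section 12 the research assistants deliver the self-report assessments. These include self-reported dental visiting, one of the two measures being considered as primary outcome for the definitive trial. Under Section 20 the outcome data are summarised to help plan that trial. Second, whether research assistants can be kept blind is itself a question for the qualitative study, so the blinding procedure under examination should be stated correctly. A later protocol that borrowed this section would also inherit the error.

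**Working it through.** There is no figure to reproduce. The check is a comparison of texts.

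1. **Commitment against rule, within Section 17.** The commitment is that assessors are blind. The rule is that, after a break and where possible, a second researcher who is unblinded finishes the assessment. The two cannot both hold for the replacement assessor.

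2. **Does the literal rule have a purpose?** If an unblinded assessor were acceptable, the first researcher could simply carry on. Calling in a second person helps only if that person is still blind. The literal wording therefore removes the reason for the swap.

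3. **Direction of the other text.** The same paragraph wants fewer blind breaks ("reduce further blind breaks"). Section 32 protects the blind at PPI meetings and Section 34 protects it in contacts with participants. Nothing in the protocol calls for unblinded assessors. All of this points to blinded as the intended word.

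4. **Is the rule corrected elsewhere?** Sections 32 and 34 are general reminders and do not say who assesses after a break. Section 33 states a research aim, not a procedure. Section 18 (Data collection methods) covers the mode of assessment and training, not replacement of assessors. The table of amendments, with entries for versions 5 and 6, does not mention Section 17. The SAP supplied describes a different trial, of an imagery intervention for students at risk of suicide, so it cannot settle the matter either way.

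5. **What does the rule feed into?** Section 20 states: "Analyses of intervention efficacy will not be investigated, but outcome data will be summarised to inform a definitive trial". The traffic-light criteria in Section 12 concern recruitment, availability of visiting data, completion of the dental examination and receipt of at least one intervention session. None of them uses blinding status.

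6. **How often would the rule apply?** Only after a blind break, and only where a second researcher is available. Neither document gives an expected rate of blind breaks, so no count of affected assessments follows.

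**The case against.** The strongest reply is that this is a one-word typing error with an obvious meaning. The opening sentence of Section 17 governs, staff would be unlikely to bring in a second unblinded colleague on purpose, and the outcomes are only described. That reply stands as far as size is concerned. It does not make the sentence correct, and an instruction to staff should not depend on the reader's repairing it.

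Three stronger readings are tempting, and the documents support none of them.

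- *A reader might infer that the reassignment rule is the only step after a blind break.* It is not. Section 17 also requires each break to be recorded on a structured form and reviewed by the senior management team and the TSC. It is only the sole rule on who completes the assessment.
- *A reader might infer that the trial knowingly accepts unblinded assessment.* The opening sentence of Section 17 says the opposite, and the remarks on blinding elsewhere all aim to protect the blind.
- *A reader might infer that the nine-month results will be biased.* The documents show no route from this word to a bias of any stated size. The items that research assistants deliver are participants' own reports, the protocol describes blinding only for researchers, the rule is conditional, and no comparison of efficacy is planned.

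**Conclusion.** The point holds as a minor internal contradiction: an operative rule in Section 17 is wrong as written. That the intended word was blinded is an inference, but a well-supported one, since the rule has no purpose on any other reading.

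The effect on this trial is small. Blind breaks are tracked and reviewed whatever this sentence says, outcomes are reported descriptively, and the decision to progress does not turn on blinding. The case for correcting it is that the sentence instructs staff, that the feasibility of blinding is under study, and that the correction costs almost nothing. The conclusion assumes that the printed sentence is the protocol's own wording; nothing suggests a redaction or a fault in reading the PDF.

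**What to change.** Reword the sentence so that the replacement assessor is blind and keep the qualifier, for example: *Where possible, if an assessor becomes unblinded, a second researcher who remains blind to allocation will complete that assessment.*

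The cost is one sentence, with no change to design, staffing, data collection or analysis. Section 25 requires protocol changes to go to the REC as an amendment, so the correction can be included in the next one. There is a precedent for bundling of this kind: the version 6 entry in the table of amendments put right an inconsistency in the age criterion alongside a recruitment extension.
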